---

# **1 Introduction**

## ***1.1 Study Abstract***

The prevalence of obesity has increased dramatically in the United States over the last two decades, with rapidly rising and premature adverse health consequences. Women of reproductive age, especially overweight and obese (OW/OB) minorities and those of low socioeconomic status, are at risk of adverse pregnancy outcomes due to excessive gestational weight gain (GWG) and this further contributes to alarming rates of childhood obesity and diabetes. Preventing excessive GWG could reduce pregnancy complications and improve long term health of women and their offspring. Weight control studies in pregnancy are emerging but most studies have emulated traditional weight control programs through diet counseling or increased activity but with limited evidence of sustained adherence. Novel approaches are needed to limit weight gain to new Institute of Medicine (IOM) goals, and to help OW/OB mothers adhere to recommended diet, physical activity and lifestyle behaviors that they can model for their families. The proposed research will develop and test a new approach to primary and secondary prevention of obesity through a behaviorally adapted, nutrient-dense, energy-balanced lifestyle that can be implemented clinically, assessed objectively and sustained long term through technologically-advanced self-monitoring methods. This randomized controlled clinical trial compares with standard care, as a continuous variable the GWG of OW/OB pregnant women who participate in lifestyle intervention with individualized, motivational coaching and group sessions to develop self-monitoring of recommended diet and physical activity behavior long term. Anthropometric, metabolic, diet, activity and lifestyle outcomes will be assessed prenatally and for at least 12 months post-delivery. The birth outcome, diet, and growth of the infant will also be measured. The Northwestern Department of Obstetrics and Gynecology provides care for over 12,000 ethnically diverse obstetric patients a year, many of whom participate in clinical trials, facilitated by a highly functional obstetric research infrastructure. Our multidisciplinary team, experienced in obstetrics and prevention research, propose innovative technology, personalized nutrient goals and enhanced self-monitoring skills to document whether excess gestational weight gain can be avoided and if new mothers can successfully develop and model energy-balanced diet and lifestyle behaviors for their families, thereby reducing and preventing obesity long term.

## ***1.2 Study Objective***

To test, in 300 ethnically diverse OW/OB pregnant women, a behavioral intervention aimed at controlling GWG through recommended diet, activity and lifestyle changes that are to be maintained postpartum.

## ***1.3 Hypothesis***

GWG will be less among the Intervention group vs. Usual Care (control) group.

## ***1.4 LIFE MOMS Consortium***

This randomized clinical trial is one of the studies conducted by the LIFE-Moms Consortium. The Consortium is a collaborative study group with the goal of testing different behavioral/lifestyle interventions in overweight and obese pregnant women in separate trials while providing for the ability to combine data from the individual trials by harmonizing interventions, trial design elements, study procedures and data collection. Key measures and procedures that will be common to all of the trials are designated as ‘Core’ and will provide the basis for Consortium wide evaluations. ‘Super Shared’ measures and procedures are defined as those collected on 4 or more of the LIFE-Moms trials. ‘Shared’ measures and procedures are defined as those collected on 2-3 of the LIFE-Moms trials.

## 2 Background

### 2.1 Incidence and Etiology / Burden of Disease

#### Significance

**Maternal Overweight/Obesity and Adverse Metabolic Outcomes.** The prevalence of maternal overweight and obesity has nearly doubled in the United States since 1976 [1]. In 2004-2005, 42% of pregnant women had body mass index (BMI) above 25 versus 23% in 1993 [2]. Gestational weight gain (GWG) over 40 pounds has steadily increased since 1990, and estimated mean postpartum weight retention among women who gained above IOM Guidelines ranges from 10 pounds to over 20 pounds [3]. Excessive GWG increases BMI at subsequent pregnancies with increased long term risk of cardiovascular diseases, cancer and overall metabolic health [3-5]. Adverse maternal-offspring consequences independently associated with excessive GWG include preeclampsia, impaired glucose tolerance, cesarean delivery, large for gestational age (LGA) infants (birthweight  $\geq 90^{\text{th}}$ ile), and fetal macrosomia (birthweight  $>4,000\text{gms}$ ), as well as obesity in childhood, adolescence, and early adulthood [6-9]. Excessive GWG is also associated with increased systolic blood pressure, levels of C-reactive protein (CRP) and interleukin-6 (IL-6) and decreases in HDL- cholesterol (HDL-C) in offspring [9-15]. The mechanisms underlying this “fetal programming” are unclear, but may include fetal overnutrition from elevated circulating maternal concentrations of glucose and fatty acids, exposure to elevated concentrations of insulin and leptin/adiponectin or other factors affecting the development of the hypothalamic pathways that regulate appetite, body weight, and/or epigenetic effects related to maternal diet [16].

Left uninterrupted, this cycle of perpetual excessive GWG with increasing adverse maternal-offspring consequences could have a devastating public health impact. This prompted the IOM to reexamine and revise the GWG Guidelines in 2009 with limits of 15-25 pounds (7-11.5 kg) in overweight (BMI 25.0-29.9 kg/m^2) and 11-20 pounds (5-9 kg) in obese (BMI  $\geq 30.0$  kg/m^2) women [3]. Lifestyle modifications which have been proven effective among non-pregnant populations [17, 18] have been applied to prevention of excessive GWG in overweight or normal weight women, and the results have been promising in some [19-21] but not all studies [22, 23]. Research is urgently needed to identify and apply effective approaches to lifestyle modification including electronic, technologically enhanced approaches that can be successfully adapted to OW/OB pregnant women of diverse ethnic, racial and economic backgrounds.

### 2.2 Potential for Prevention

**Studies on Prevention of Excessive GWG: Results and Limitations.** Behavioral interventions on diet and increased physical activity in nonpregnant obese adults have successfully achieved weight loss and improved clinical outcomes, such as reduced incidence of type 2 diabetes (T2D); but far less is known about behavioral interventions in pregnant women. Trials conducted to date have yielded mixed results; some but not all intervention trials have succeeded in reducing GWG in OW/OB women [24-27]. Pre-pregnancy BMI, smoking habits, race, income and number of prior pregnancies were all associated with GWG, but not all studies controlled for these factors [22, 24-27]. One randomized controlled trial (RCT) among low income women, intervened with biweekly newsletters, personalized weight gain charts and individualized nutrition counseling and reported decreases in GWG among normal weight but not overweight women [22]. More recent results using a similar intervention also reported improved postpartum weight loss maintenance in both normal weight and OW/OB women [28]. Conversely, intervention with educational radio broadcasts, pamphlets, supermarket tours, cooking demonstrations, exercise groups and individual counseling geared toward healthy diet and exercise during pregnancy was

not associated with significantly reduced GWG compared to the control group [24]. Reduction of GWG in a low income subgroup of normal and OW women was achieved by charting weight gain and providing five 1-page mailings about healthy eating and exercise during pregnancy [25]. A Finnish study that individualized counseling on diet and physical activity following five routine OB clinical visits along with group exercise sessions did not affect excessive GWG but intake of vegetables, fruit and dietary fiber increased [27]. Still another study reported reduced GWG in OB women through weekly 30-minute individual motivational sessions and aqua aerobic classes designed for OB women conducted by nurse midwives [29]. While these studies offer potential promise, well-designed studies with adequate power and standardized methods are needed to enhance adherence to lifestyle interventions and document reductions in excessive GWG in large, ethnically diverse populations and also sustain these behavioral changes postpartum.

**Lifestyle Interventions on Diet, Physical Activity and Weight Loss in Non-pregnant Populations: Applications for Prenatal Intervention.** Complex interactions between environment, genes and psychological factors occur throughout the lifespan [30]. Virchow called this “disturbances of human culture” [31]. Unfavorable exposures in the modern environment are important considerations in attempting lifestyle change. In non-pregnant OW/OB adults, restricted energy intake and increased energy output are key to achieving weight loss goals [32, 33]. Obesity often reflects an overfed and undernourished paradox with adverse maternal-offspring consequences. Lifestyle interventions to safely reduce GWG must be both nutrient-dense and energy balanced. The Diabetes Prevention Program (DPP) successfully reduced development of diabetes by 58% in non-pregnant OW/OB adults with prediabetes by weight loss through reduced-calorie diet (30% fat, 40% carbohydrate and 30% protein) and increased physical activity (goal of 150 minutes of moderate activity per week) [34, 35]. Originally DPP was individually delivered; later group-based and more cost effective [36, 37]. Likewise, the PREMIER trial focused on reducing blood pressure among free-living individuals through increased physical activity and weight loss through the Dietary Approaches to Stop Hypertension (DASH) study diet with 2,300 mg sodium [38]. Classes taught how to follow the DASH diet and include 180 minutes per week of moderate intensity physical activity through behavior change strategies that enhanced adherence. Self-monitoring using written records, individualized feedback, problem solving and ongoing social support contributed to success. Greater adherence was reported at 6 months versus 18 months, but the 5-6% weight lost by both physical activity only and the exercise plus DASH intervention groups was retained by 75% of these participants (- 4.3 kg vs. -3.8 kg, respectively, versus control, -1.5 kg) long term [18]. Further evidence of the efficacy and safety of this intervention has been reported in a DASH diet trial among adolescents (41). To our knowledge neither the DASH diet nor the multi-component interventions applied within the PREMIER or DPP studies combined with electronic self-monitoring of behavior have been previously tested in OW/OB pregnant or postpartum women.

## 3 Study Design

### 3.1 Primary Research Question

Can prenatal diet and lifestyle intervention among overweight/obese pregnant women reduce gestational weight gain? For the purpose of this primary outcome, gestational weight gain is defined as the difference between the maternal weight measured at the 36 week visit and the weight recorded at the Baseline visit.

### 3.2 Secondary Research Questions

- Will adherence to the DASH diet and lifestyle intervention, in addition to reduced GWG, also produce postpartum weight control and other beneficial outcomes related to the following parameters?
- Will metabolic profiles (blood pressure, anthropometry, fasting glucose, insulin or C-peptide, HbA1c, blood lipids and CRP) of mothers and babies be different between the Intervention and Usual Care groups?
- Will prenatal diet and lifestyle intervention in overweight/obese mothers result in fewer complications of pregnancy (preeclampsia, gestational diabetes mellitus (GDM), cesarean birth)?
- Will infants in the Intervention group breastfeed longer, begin solid foods later and have higher quality diets (more fruits, vegetables, dairy, less sugary beverages) than Usual Care group infants at 12 months?
- Is adiposity (percent body fat) and body weight reduced postpartum in mothers and babies in the intervention group compared to Usual Care?
- Do mothers in the Intervention group have higher quality diet (more fruits, vegetables, grams of fiber and nonfat dairy; less saturated fat/trans fat, sugar sweetened beverages) and more minutes of physical activity than mothers in the Usual Care group throughout the study?
- Will diet quality differences be evident as measured by metabolomics assays specifically related to fruit/vegetable and dietary fiber intake as alkylresorcinols (fiber), prolinebetaine (citrus fruit) and S-methyl-L-cysteine sulphoxide (cruciferous vegetables) in maternal urine and cord blood.
- Are measures of sleep quality and duration, depression and stress, self-efficacy and mindfulness in diet, breastfeeding and physical activity more favorable in the intervention group compared with the Usual Care group?

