### **3.4.4 Exclusion Criteria**

-IVF conception/ovulation induction w/ gonadotropins

-Weight gain of >15 pounds from reported pre-pregnancy weight to Baseline visit

-Current smoker

-Prior bariatric surgery

-In weight loss program w/in 3 months of conception

-History of alcohol or drug abuse within 5 years

-No access to internet and/or smartphone

-Unable to attend intervention/follow-up visits

-Unwilling/unable to commit to self-monitoring data collection

-Unable to complete intervention program

-Presence of any condition that limits walking or following diet recommendations

-Not fluent in English

-Diagnosis of diabetes prior to pregnancy, or an Hb A1c  $\geq 6.5$  % or other test result suggestive of pre-pregnancy diabetes. All potential participants will have Hb A1c performed prior to randomization.\*

-Known fetal anomaly \*

-Planned termination of pregnancy\*

-History of three or more consecutive first trimester miscarriages\*

-Past history of anorexia or bulimia by medical history or patient report. Binge eating disorder (BED) is not an exclusion.\*

-Current eating disorder diagnosed by EDE-Q questions 2-4 and confirmed after discussion with the participant by study staff\*

- Actively suicidal defined as a value  $\geq 2$  on the BDI-II question 9\*
- Prior or planned (within 1 year of expected delivery) bariatric surgery\*
- Current use of one or more of the following medications: \*
  - Metformin
  - Systemic steroids
  - Antipsychotic agents (e.g., Abilify, Haldol, Risperdal, Seroquel, Zyprexa)
  - Anti-seizure medications or mood stabilizers that would be expected to have a significant impact on body weight (e.g., Depakote, Lamictal, Lithium, Neurontin, Tegretol, Topamax, Keppra)
  - Medications for ADHD including amphetamines and methylphenidate
- Continued use of weight loss medication including over the counter (OTC) and dietary supplements for weight loss (e.g., Adipex, Suprenza, Tenuate, Xenical, Alli, conjugated linoleic acid, Hoodia, Green tea extract, Guar gum, HydroxyCut, Sensa, Corti-slim, Chromium, chitosan, Bitter orange) \*
- Contraindications to moderate to high intensity physical activity in pregnancy specified in the ACOG Committee Opinion #267, 2002 (reaffirmed 2009) \*
  - Hemodynamically significant heart disease defined as an AHA class II (short of breath with exercise) or greater
  - Restrictive lung disease (e.g. pulmonary fibrosis)
  - Poorly controlled hyperthyroidism

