  - Poorly controlled seizure disorder
  - Poorly controlled hypertension defined as a blood pressure  $\geq 160/110$
  - Current extreme sedentary lifestyle (e.g. bed bound)
  - Orthopedic limitations to aerobic exercise
  - Severe anemia defined as a hemoglobin  $< 8$  or hematocrit  $< 24$
- Participation in another interventional study that influences weight control\*
- Enrollment in this trial in a previous pregnancy\*
- Intention of the participant or of the care provider for the delivery to be outside the LIFE-Moms Consortium hospital\*
- Participant's unwillingness or inability to commit to a 1 year follow-up of herself or her child, including planning to move away.\*

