### ***3.6 Randomization Method and Masking***

The randomization will be done using a permuted block design with variable block sizes. In addition to simple randomization this tends to produce groups comparable with respect to known and unknown risk factors and will also ensure that groups are roughly the same size at any point during recruitment which will eliminate the possibility of differential bias due to seasonality. No planned stratification levels are pre-specified. Allocation concealment to the study coordinator will be ensured up to the point of randomization.

Prior to recruitment, a randomization vector (list) reflecting the permuted block design described above is prepared and uploaded to the study tracking system (as a table in an MS Access database). This randomization vector simply gives the random order in which participants are to be placed in either the intervention or control group. When a stratified design is employed, a separate randomization vector is defined for each strata. These vectors are produced via SAS Proc PLAN or with use of random numbers generated in MS Excel depending on the complexity of the study. The randomization table in the Access database is shielded from view by study staff so that it is not possible for staff to view the table during the trial.

As prospective participants are encountered, a recruitment/randomization form in the Access database is opened and populated with status codes indicating study eligibility. Checkboxes and drop down lists are provided for each study component necessary for enrollment into the study (e.g., boxes for completed pre-randomization measures, exclusion criteria, run-in completion, etc. are shown on the recruitment form). The form contains a randomization button: Initially, the button is not enabled, its color is grey, and the button caption is reads “Please Enter All Eligibility Criteria.” As participants complete the pre-randomization study components, information is entered into the recruitment screen by study staff. When the information entered indicates that the participant is ineligible to be randomized, the randomization button caption is set to “Ineligible,” the button turns red, and it remains un-enabled. When all the information has been entered and the codes indicate that the participant is eligible for randomization, the button text changes to “Eligible, Press to Randomize,” the button turns green, and it is enabled by the underlying program.

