#### ***4.3 Baseline procedures***

Study Coordinator will initiate a phone, text or email reminder prior to the Baseline visit, which will be conducted with the participant fasting. The Study Coordinator will explain the study and obtain written informed consent among interested participants. Standardized questionnaires (listed in Section 4.4.3) will be administered to ascertain prenatal and demographic data. Height, weight and blood pressure will be measured by trained staff. Eligible women will be asked to conduct a supervised, self-administered 24-hour diet recall (ASA24 online <https://asa24beta.westat.com/ResearcherSite.html>) and complete sleep/stress/other questionnaires. Assistance will be offered if needed. Women will be instructed how to wear the Actigraph for the subsequent 7 days. Urine and blood will be collected. HbA1c will be measured and storage samples for future measures, including fasting glucose, insulin, adiponectin, IL-6, lipids, CRP and 25-hydroxyvitamin D will be collected. The Randomization visit will be scheduled within 1-2 weeks.

In addition to information collected for eligibility, the following data will be obtained from the participant and chart review:

- Demographic information: maternal date of birth, race and ethnicity, marital status, family size, household type, income, occupational status, TV, telephone and computer ownership, internet/computer access, cell phone usage and technology, maternity leave, education/literacy.
- Paternal demographic information: age at maternal enrollment, race, ethnicity, body type as identified by participant using standard silhouettes
- Medical history: self-reported pre-pregnancy weight, underlying medical conditions, current medications; family history of diabetes and hypertension
- Obstetrical history: to include gravidity, parity, and a description of previous births (year, birth weight, gestational age at delivery, weight gain, gestational diabetes, preeclampsia, birth trauma. A Modified-Pregnancy-Unique Quantification of Emesis and Nausea Index (PUQE) questionnaire, which assesses the severity of nausea and vomiting of pregnancy, will be given at baseline.
- Social history: alcohol use, tobacco use

**Blood Pressure (BP).** Seated BP will be measured after a 5 minute rest according to a standardized protocol.

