#### ***4.7.2 Maternal Secondary Outcomes***

a) gestational diabetes

- b) preeclampsia
- c) cesarean delivery
- d) shoulder dystocia
- e) weight, adiposity, BP, fasting glucose, lipids, C-reactive protein, vitamin D, leptin, adiponectin
- f) Homeostatic Model Assessment (HOMA) score, a measure of insulin resistance (with the assistance of a computer program available online from the University of Oxford Diabetes Trial Unit)
- g) diet quality (diet and metabolomics assessment)
- h) physical activity
- i) sleep quality and duration
- j) measures of stress and self-efficacy

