### ***5.4 Analysis Plan***

All statistical analyses will be based upon the total cohort of patients randomized into the trial. Although data on some patients may be missing, all relevant data available from each patient will be employed in the analyses. Patients will be included in the treatment group to which they were randomly assigned regardless of the adherence to the intervention.

The primary analysis will consist of a simple comparison of GWG using an independent t-test. While this is a longitudinal study, and taking advantage of second trimester weights would be a more powerful analysis, there is currently no indication that the pattern of weight gain (whether excess weight gain occurs in the second trimester or third) is associated with worse outcomes. As the intent of this trial is to limit GWG, the analysis is designed to specifically address the comparison of mean weight gain in the two groups. Mean and standard deviation of weight gain will be reported. If the groups are found to differ on a pre-treatment factor known to be a factor related to weight gain, the statistical analysis will adjust for these differences using a multiple linear regression model. Additionally, adjusted means and confidence intervals will be presented after adjusting for factors such as age, pre-pregnancy BMI, and race.

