#### ***5.4.1 Methodology***

In general, analyses of data will be conducted to address the primary and secondary research questions of the trial, and other interrelationships among elements of study data of interest to the investigators and of relevance to the objectives of the study. Specifically when comparing groups multiple linear or logistic models will be fit. A further exploration of weight gain and retention will be examined using mixed models to determine if the patterns of weight gain and loss are similar across the two groups.

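### Cesarean delivery is a secondary outcome, but the plan does not commit to recording previous mode of delivery or to using it in the analysis, which may cost precision

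*Combined protocol and SAP*

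**What the plan says.** Cesarean appears twice as an outcome. Section 3.2 asks whether the intervention will "result in fewer complications of pregnancy (preeclampsia, gestational diabetes mellitus (GDM), cesarean birth", and section 4.7.2 lists "cesarean delivery" without separating first from repeat operations.

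The exclusions in section 3.4.4 that concern past pregnancies are "History of three or more consecutive first trimester miscarriages" and "Enrollment in this trial in a previous pregnancy". Neither limits parity or excludes a previous cesarean. Section 4.3 collects gravidity, parity and "a description of previous births (year, birth weight, gestational age at delivery, weight gain, gestational diabetes, preeclampsia, birth trauma", so parous women are expected. Mode of delivery is not among these items.

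On randomization, section 3.6 states: "No planned stratification levels are pre-specified". On analysis, section 5.4 provides for adjustment "If the groups are found to differ on a pre-treatment factor known to be a factor related to weight gain", and gives age, pre-pregnancy BMI and race as examples of covariates for adjusted means. Both provisions concern weight gain. For other group comparisons section 5.4.1 says: "Specifically when comparing groups multiple linear or logistic models will be fit". It names no covariates.

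**The concern.** The section 3.2 question names three complications. For two of them, preeclampsia and gestational diabetes, section 4.3 lists the woman's own history. For the third, cesarean, the matching item would be how she delivered before, and it is not listed.

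Suppose many women with a previous cesarean have another, for reasons that a diet and walking programme changes little. These women then add events to both arms. The overall difference shrinks and the variance grows. Randomization keeps the comparison valid, but the trial is less able to detect a reduction among the women in whom one could occur. A recorded and pre-specified delivery history would recover part of that precision.

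**Working it through.** **The plan's own figures.** No rate, effect size or power is given for cesarean, and the complication composite in Table 5 does not include it, so there is no cesarean figure to reproduce. The primary sample size does reproduce: with a difference of 5 lb, an SD of 15 lb, two-sided 0.05 and 80% power, the t-test needs 142.2, rounded up to the stated 143 per group.

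**Inputs from section 5.2.** 150 per arm with at most 10% attrition for delivery outcomes gives n = 150 × 0.90 = 135 per arm. The test is two-sided at 0.05.

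**Assumed inputs (not in the documents).** Share with a previous cesarean f = 10-25%. Repeat rate R = 80-90%, the same in both arms. In the other women, control rate b = 30% and intervention rate t = 15%, 20% or 25%.

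**Formulas.**
- Pooled rates: pc = fR + (1−f)b and pt = fR + (1−f)t, with mean p.
- Pooled power: Φ{[(pc−pt) − 1.96·√(2p(1−p)/n)] / √([pc(1−pc)+pt(1−pt)]/n)}.
- Stratified power: difference d = (1−f)(b−t). With m = (b+t)/2, the null variance is V0 = [(1−f)·2m(1−m) + f·2R(1−R)]/n. The alternative variance is V1 = [(1−f)(b(1−b)+t(1−t)) + f·2R(1−R)]/n. Power is Φ{(d − 1.96√V0)/√V1}.

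**Worked case: f = 20%, R = 90%, 30% versus 15%.**
- pc = 0.18 + 0.24 = 0.42 and pt = 0.18 + 0.12 = 0.30. A 15-point difference (risk ratio 0.50) becomes 12 points (risk ratio 0.71).
- Pooled: (0.12 − 1.96 × 0.0584)/0.0580 = 0.09, power 54%. With no previous cesareans it would be 84%.
- Stratified: V0 = (0.279 + 0.036)/135 = 0.002333 and V1 = (0.270 + 0.036)/135 = 0.002267. Then (0.12 − 1.96 × 0.0483)/0.0476 = 0.53, power 70%.
- Restricted to the 108 per arm without a previous cesarean: power about 75%.

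**Range.** The first six rows are the ends of the assumed range for each effect. The last two lower the repeat rate to 60%.

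| Other women | Share f | Repeat R | Pooled | Stratified | Gain (points, about) |
|---|---|---|---|---|---|
| 30% vs 15% | 10% | 80% | 69.5% | 76.4% | 7 |
| 30% vs 15% | 25% | 90% | 47.3% | 65.8% | 18 |
| 30% vs 20% | 10% | 80% | 36.1% | 40.5% | 4 |
| 30% vs 20% | 25% | 90% | 23.9% | 33.1% | 9 |
| 30% vs 25% | 10% | 80% | 12.0% | 13.0% | 1 |
| 30% vs 25% | 25% | 90% | 9.0% | 11.1% | 2 |
| 30% vs 15% | 10% | 60% | 71.5% | 74.4% | 3 |
| 30% vs 15% | 25% | 60% | 50.9% | 56.3% | 5 |

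Simulation with a Cochran-Mantel-Haenszel test agrees to within about one point. In the second row it gives a gain of 17.7, so the range is quoted as 7-18.

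**Check on the no-effect assumption.** If the relative effect were the same in women with a previous cesarean (90% falling to 45%, f = 20%, 30% versus 15% in the others), pooled power is about 96%, stratified 98% and restricted about 76%. Dilution disappears. Stratifying still does no harm, but restricting loses power.

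**The case against.** Several points on the other side stand.

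- **Both lists are open.** The history items in section 4.3 and the covariates in section 5.4 are introduced as inclusions or examples. Chart review is planned, and section 6.1 leaves the forms to be developed. A reader might infer that previous mode of delivery is unavailable or barred from the models. The documents do not support that; they only make no commitment to record or use it.
- **The named covariates belong to the weight-gain analysis.** They neither define nor limit a cesarean model. Section 5.4.1 leaves covariates unspecified for every outcome, and a logistic model with delivery history fits its wording.
- **The driving facts are assumed.** The documents do not say how many women have had a cesarean, how often it is repeated, or how strongly it predicts the outcome. Calling it the strongest baseline predictor would go beyond them.
- **The largest gains need a large effect.** They assume that the programme halves cesarean in the other women. At smaller effects the comparison is underpowered under any of these analyses, and stratifying would not rescue a null result.
- **All cesareans in all randomized women is a legitimate question.** Restricting to women without a previous cesarean answers a narrower one.
- **The stakes are low.** This is one secondary outcome with no power claim.

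What remains is a specific, inexpensive omission. Stratifying raised power in every setting tried, and a covariate fixed in advance is more credible than one chosen after results are seen by arm.

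**Conclusion.** The point holds as an optional gain in efficiency. The plan makes cesarean a secondary outcome in a population that may include women with a previous cesarean, and commits neither to recording previous mode of delivery nor to using it. A reader might infer that the cesarean comparison is biased, or that a null result would be explained by repeat operations. Neither follows: the whole-cohort comparison is valid, and the loss of precision depends on repeat cesarean being common and little changed by the intervention.

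Under the assumed shares and 80-90% repeat rates, the gain from stratifying runs from about 1-2 points (30% versus 25%) to about 7-18 points (30% versus 15%). With a 60% repeat rate it is at most about 5 points. The primary weight-gain analysis and Table 5 are untouched.

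**What to change.** In section 4.3, add mode of each previous delivery to the obstetric history, abstracted from the chart already under review and retrospectively where women are already enrolled.

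In section 5.4.1, before outcomes are compared by arm, pre-specify that cesarean delivery in all randomized women is analysed stratified by, or adjusted for, delivery history in three groups: nulliparous, parous without a previous cesarean, and previous cesarean. Report cesarean among women without a previous one as a supporting result only.

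The cost is one abstracted field and a sentence or two in the analysis plan. The supporting result uses fewer women and answers a narrower question, so it should not replace the whole-cohort comparison.
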